4.1.4 Subject Enrollment and Randomization

Study participation begins (ie, a subject is “enrolled”) once written informed consent is obtained. Once informed consent is obtained, a subject identification (SID) number will be assigned by a central system (eg, an interactive voice/web response system [IXRS], and the screening evaluations may begin to assess study eligibility (inclusion/exclusion) criteria. The SID number will be used to identify the subject during the screening process and throughout study participation, if applicable.

A master log of all consented subjects will be maintained at the site and will document all screening failures (ie, subjects who are consented but do not meet study eligibility criteria), including the reason(s) for screening failure.

Subjects who fail to meet the inclusion/exclusion criteria (ie, screening failures) should not be randomized (if applicable) or receive investigational product. Subjects who are randomized but do not receive MEDI5884 or placebo may be rescreened.

Subjects may be rescreened once to permit eligibility based on time-dependent factors including:

- Not being on a stable dose of high-intensity statin therapy for the required [REDACTED] (inclusion criterion 7)
- Not being at least [REDACTED] since an unstable cardiovascular condition (exclusion criterion 11)
- To permit a change in antihypertensive therapy so that clinically significant bp abnormalities have resolved ([REDACTED])
- To be at least [REDACTED] out from lipid-lowering medication not permitted in [REDACTED]
[REDACTED]
- To be on a stable dose of thyroid hormone for at least [REDACTED] prior to screening ([REDACTED])
- To have been off of systemic corticosteroids for at least [REDACTED] prior to screening ([REDACTED])
- To avoid having had a severe infection or ongoing febrile illness within [REDACTED] of screening ([REDACTED]).

Rescreening to meet laboratory- or ECG-based enrollment criteria is not permitted with the following exception:

- Subjects who were excluded based on fasting triglyceride or LDL-C levels may be rescreened once if their lipid-lowering therapy has been increased; rescreening must be [REDACTED] after change in therapy.

4.1.5 Withdrawal from the Study

Subjects are free to withdraw their consent to participate in the study (investigational product and assessments) at any time, without prejudice to further treatment. Subjects who withdraw consent will be asked about the reason(s) and the presence of any adverse events (AEs). If the subject is willing, the subject will be seen and assessed by the investigator. Adverse events will be followed up; and all study medications should be returned by the subject. If a subject withdraws from further participation in the study, then no further study visits or data collection should take place.

4.1.6 Discontinuation of Investigational Product

An individual subject will not receive any further investigational product if any of the following occur in the subject in question:

1. Withdrawal of consent from further treatment with investigational product or lost to follow-up
2. An AE that, in the opinion of the investigator or the sponsor, warrants discontinuation of further dosing
3. Subject is determined to have met one or more of the exclusion criteria or failed to meet all of the inclusion criteria for study participation at study entry and continuing investigational product might constitute a safety risk
4. Subject noncompliance that, in the opinion of the investigator or sponsor, warrants withdrawal (eg, refusal to adhere to scheduled visits)
5. Pregnancy in any female subject
6. Any of the following liver function abnormalities: ALT or AST $\geq 3 \times$ ULN and total bilirubin $> 2 \times$ ULN
7. Subject's most recent apoB value, obtained at least [REDACTED] after the subject's previous dose, exceeds his or her baseline ([REDACTED] predose) level by ≥ 30 mg/dL. ApoB testing may be repeated once within the protocol-specified dosing window for Doses 2 or 3, and if that value is < 30 mg/dL higher than the baseline value, the subject may be dosed. If the subject's apoB level is ≥ 30 mg/dL above the baseline level the subject cannot be dosed but will remain in the study to be followed for safety.
8. Subject's pre-dose triglyceride value is ≥ 1000 mg/dL.

Subjects who are permanently discontinued from receiving investigational product will be followed for protocol-specified assessments, including follow-up of any AEs, unless consent is withdrawn from further study participation (Section 4.1.5).

4.1.7 Replacement of Subject

Subjects who do not complete dosing per randomization for any reason other than for safety (which includes subjects who withdrew due to an AE or by having met withdrawal criteria for withdrawal of investigational product (Section 4.1.6) may be replaced if deemed necessary by the medical monitor to ensure that safety and PK data are collected from a sufficient number of subjects and to maintain the balance of the study.

4.1.8 Withdrawal of Informed Consent for Data and Biological Samples

4.1.8.1 Biological Samples Obtained for the Main Study

Study data are protected by the use of an SID number, which is a number specific to the subject. The investigator is in control of the information that is needed to connect a study sample to a subject. A subject's consent to the use of data does not have a specific expiration date, but the subject may withdraw consent at any time by notifying the investigator. If consent is withdrawn, any samples collected prior to that time may still be given to and used by the sponsor but no new data or samples will be collected unless specifically required to monitor the safety of the subject.

4.1.8.2 Samples Obtained for Genetic Research or Future Research

Samples obtained for genetic research or future research will be labeled with a sample identification number linked to the SID number but will not be labeled with personal identifiers such as the subject's name. If the subject withdraws consent for participating in genetic research or future research, the sponsor will locate the subject's sample and destroy it. The coding of samples and results is to ensure that these research results are kept confidential by keeping the subject's identity and these results separate.

If the subject consents to have his/her samples used for genetic research or future research, this additional research may not start immediately and may start at any time during the storage period. The subject's sample(s) including any specimens of extracted DNA will be stored by the sponsor with similar samples from other subjects at a secure central laboratory. The subject's samples will not be kept for more than 25 years after the end of the study in which they were collected. If the subject chooses not to allow his/her study samples to be used for genetic research or future research, the samples will be destroyed by the sponsor once they are no longer required for the main study.

If consent is withdrawn after a sample has been taken but before the subject's sample is sent to the sponsor for genetic research or future research, the investigator will arrange to have it destroyed. If consent is withdrawn after the subject's sample(s) have been sent to the sponsor for genetic research or future research, the sponsor and the investigator will ensure that these sample(s) are destroyed unless the sample identification number has been removed and the subject can no longer be linked to any sample(s). However, if the subject's samples have already been used for research, the sponsor is not required to destroy results of this research. In this case only the remaining sample(s) will be destroyed.

4.2 Schedule of Study Procedures

4.2.1 Enrollment/Screening Period

Table 4.2.1-1 shows all procedures to be conducted at Screening.

Whenever vital signs, 12-lead ECGs, and blood draws are scheduled for the same nominal time, the assessments should occur in the following order: 12-lead ECG, vital signs, and then blood draws.

Table 4.2.1-1 Schedule of Screening Procedures

Study Period	Screening
Visit Number	V1
Procedure/Study Day	[REDACTED]
Main study informed consent / assignment of SID number	X
Future use informed consent (optional)	X
Genetic research informed consent (optional)	X
Medical History	X
Body Weight	X
Height	X
Physical Examination (Detailed)	X
Vital Signs	X
dECG ^a	X
Serum Chemistry and Hematology	X
Thyroid Stimulating Hormone	X
HbA1c	X
Lipids for Eligibility ^b	X
Urinalysis	X
FSH ^c	X
Urine Pregnancy Test ^c	X
Hepatitis and HIV	X
Assessment of AEs and SAEs	X
Assessment of Concomitant Medications	X
Verify Eligibility Criteria	X
EL Mass and Exploratory Biomarkers ^b	X
[REDACTED]	[REDACTED]
[REDACTED]	[REDACTED]
[REDACTED]	[REDACTED]
c	[REDACTED]

4.2.2 Randomized Treatment Period and Follow-up

Table 4.2.2-1 shows all procedures to be conducted at the treatment and follow-up periods.

Whenever vital signs, 12-lead ECGs, and blood draws are scheduled for the same nominal time, the assessments should occur in the following order: 12-lead ECG, vital signs, and then blood draws. The timing of the first 2 assessments should be such that it allows the blood draw (eg, PK blood sample) to occur at the proper nominal time.

Table 4.2.2-1 Schedule of Randomized Treatment Period and Follow-up Procedures

Study Period	Treatment Period															Follow-up	LDL-C or Triglycerides Follow-up ^c		
	V2	V3	V4	V5	V6	V7	V8 ^a	V9 ^b	V10	V11 ^a	V12	V13	V14	V15	V16		V18	V19	V20
Visit																			
Medical history	X																		
Body weight	X																X		
Physical examination (abbreviated)	X						X			X							X		
Vital signs ^d	X	X	X		X		X			X	X	X				X	X	X	
DECG ^e	X						X			X	X	X				X		X	
Serum chemistry and hematology	X						X			X						X		X	
Urinalysis	X						X			X						X		X	
Urine pregnancy test ^{f,g}	X																		
Assessment of AEs and SAEs	X	X	X	X	X	X	X	X	X	X	X	X	X	X	X	X	X	X	X
Assessment of concomitant medications	X	X	X	X	X	X	X	X	X	X	X	X	X	X	X	X	X	X	X
Verify eligibility criteria	X																		

Table 4.2.2-1 Schedule of Randomized Treatment Period and Follow-up Procedures

Table 4.2.2-1 Schedule of Randomized Treatment Period and Follow-up Procedures

Study Period	Treatment Period															Follow-up	LDL-C or Triglycerides Follow-up ^c		
	V2	V3	V4	V5	V6	V7	V8 ^a	V9 ^b	V10	V11 ^a	V12	V13	V14	V15	V16	V17	V18	V19	V20
Visit																			
Future use blood sample	X						X			X				X		X			
Genetic research sample	X																		
Randomization	X																		
Assessment of injection sites ^m	X	X					X	X		X	X								
Physical examination (detailed)																X			

Table 4.2.2-1 Schedule of Randomized Treatment Period and Follow-up Procedures

Figure 1 is a timeline diagram showing the study period, treatment period, follow-up period, and LDL-C or triglycerides follow-up. The timeline is represented by a horizontal axis with vertical dashed lines indicating specific points in time. The study period is divided into visits (V2, V3, V4, V5, V6, V7, V8^a, V9^b, V10, V11^a, V12, V13, V14, V15, V16, V17, V18, V19, V20). The treatment period is indicated by black bars above the timeline, with specific treatments labeled V8^a, V9^b, and V11^a. The follow-up period is indicated by white bars below the timeline, starting from V17 to V20. The LDL-C or triglycerides follow-up is indicated by blue text in the top right corner.

4.2.2.1 Early Discontinuation Visit or Unscheduled Study Visit

Study procedures should be completed as per [REDACTED]/early discontinuation visit for subjects who prematurely discontinue from the study and for subjects who require an unscheduled study visit. Subjects should be encouraged to remain in the study for follow-up.

4.2.3 Additional Follow-up

[REDACTED]

Subjects whose direct LDL-C at the [REDACTED] visit is ≥ 30 mg/dL above their baseline ([REDACTED] predose) value will return [REDACTED] after their last visit for repeat LDL-C testing, and, for continued elevation of LDL-C ≥ 30 mg/dL above Baseline, again on [REDACTED] and [REDACTED] for LDL-C testing (see [Table 4.2.2-1](#)).

Subjects whose triglyceride value at the [REDACTED] visit is > 1000 mg/dL will return for a repeat triglyceride testing on [REDACTED]. If the triglyceride value remains > 1000 mg/dL on [REDACTED], an additional follow-up visit ([REDACTED]) will occur for repeat testing ([Table 4.2.2-1](#)).

4.3 Description of Study Procedures

4.3.1 Efficacy

No efficacy assessments are being conducted in this study. PD assessments related to the effects of MEDI5884 are described in Section [4.3.6](#).

4.3.2 Medical History, Physical Examination, Height, Weight, Vital Signs, Electrocardiogram, and Injection Site Reaction Assessment

4.3.2.1 Medical History

A complete history will include medical and disease history, current medical conditions, smoking and alcohol history, past or present cardiovascular disorders, respiratory, gastrointestinal, renal, hepatic, neurological, endocrine, lymphatic, hematologic, immunologic, dermatological, psychiatric, genitourinary, drug and surgical history, or any other diseases or disorders. A medical and disease history will be performed at Screening and [REDACTED]

4.3.2.2 Physical Examination, Height, and Weight

A detailed physical examination will be performed at Screening and at last follow-up visit. The full physical examination will include examination of the following: general appearance, head, ears, eyes, nose, throat, neck, skin, heart, lung, abdomen, musculoskeletal system, endocrine system, and nervous system. An abbreviated physical exam will be performed as outlined in [Table 4.2.2-1](#). The abbreviated physical exam will include examination of: general appearance, skin, heart, lung, and abdomen, at a minimum. Each clinically significant abnormal finding will be recorded for all physical examinations. Weight and height will be measured as outlined in [Table 4.2.1-1](#) and [Table 4.2.2-1](#).

4.3.2.3 Vital Signs

Vital signs (BP, HR, respiratory rate, and body temperature) will be obtained at Screening and on study days as outlined in [Table 4.2.2-1](#). With respect to dosing, vital signs (BP, HR, respiratory rate, and body temperature) on [REDACTED] should be collected predose (within 60 minutes prior to start of dosing) and 1 hour (\pm 15 minutes) postdose. Predose vital signs should not be clinically significantly different from the subject's screening value according to the judgment of the investigator. All vital sign measurements will be measured with the subject in a supine position having rested for at least 10 minutes before each reading, and should be taken before any blood draws scheduled in close proximity

4.3.2.4 Electrocardiogram

At the visits specified in [Table 4.2.1-1](#) and [Table 4.2.2-1](#), 12-lead ECGs will be obtained after 10 minutes supine rest. Predose triplicate digital ECG on [REDACTED] should be collected at 3 different time points (3×3 replicates) prior to dosing; each triplicate must be separated by at least 5 minutes. On all other days of ECGs, they will be captured in triplicate, up to 5 minutes apart. In addition, a 10-second paper ECG print-out from the 12-lead ECGs will be taken predose, for overall evaluation (normal/abnormal) before administration and during study days. Subjects with predose ECGs showing clinically significant abnormalities, according to the judgment of the investigator, should not be dosed.

The same recorder will be used for each subject at each time point, if possible. Date and time settings should be checked at the start of each study day and aligned with an official timekeeper for all machines used in the study.

Skin preparation should be thorough and electrode positions should be according to standard 12-lead ECG placement.

The following variables will be reported: heart rate, RR, PR, QRS and QT intervals from the primary lead of the digital 12-lead ECG. Derived parameters (QTcF, QTcB, and others, as applicable) will also be calculated.

The investigator may add extra 12-lead ECG safety assessments if there are any abnormal findings or if the investigator considers it is required for any other safety reason.

4.3.2.5 Injection Site Reaction Assessment

Assessment of the injection sites for injection site reactions should be conducted as specified in [Table 4.2.2-1](#).

Subjects will be given a tape measure and an injection site worksheet. They will be instructed to record onto the worksheet whether or not an injection site reaction has occurred at any injection site during the 24 hours after each dose of investigational product. If an injection site reaction has occurred, the subject is to record the measured maximal redness and swelling and a graded assessment of pain (per [Table 4.3.2.5-1](#)) for the maximum observation at any injection site. Measurements $< \frac{1}{4}$ inch at the largest diameter should be recorded as 0 inches. Measurements $\geq \frac{1}{4}$ inch but < 1 inch would result in a subject recording “yes” to injection site reaction, but the reaction would not be graded (< Grade 1). The subject will report injection site reactions to the Investigational Site and this information will be recorded in the electronic data capture (EDC) system. The subject should return the worksheet to the site to be included in the subject’s investigational records. If the subject fails to return the worksheet, the site should query the subject, and, if the subject is able to report the information, it should be recorded, even if incomplete.

Table 4.3.2.5-1 Tables for Clinical Abnormalities: Local Reactions to Injectable Product as Reported by Subjects in their Injection Site Reaction Assessments

Local Reaction to Injectable Product	Reaction Grade			
	Mild (Grade 1)	Moderate (Grade 2)	Severe (Grade 3)	Potentially Life Threatening (Grade 4)
Pain	Does not interfere with activity	Repeated use of non-narcotic pain reliever > 24 hours or interferes with activity	Any use of narcotic pain reliever or prevents daily activity	ER visit or hospitalization
Erythema/redness ^a	1-2 inches	$> 2-4$ inches	> 4 inches	Necrosis or exfoliative dermatitis
Induration/swelling ^b	1-2 inches	$> 2-4$ inches	> 4 inches	Necrosis

Local Reaction to Injectable Product	Reaction Grade			
	Mild (Grade 1)	Moderate (Grade 2)	Severe (Grade 3)	Potentially Life Threatening (Grade 4)

ER = emergency room

- ^a In addition to grading the measured local reaction at the greatest single diameter, the measurement should be recorded as a continuous variable
- ^b Induration/swelling should be evaluated and graded using the functional scale as well as the actual measurement

Injection site reactions that occur beyond the 24 hours of collection will be recorded as AEs according to the criteria described in Section 5.1.

Investigators may choose to enter significant injection site reactions occurring during the first 24 hours postdose as AEs, but reporting of injection site reactions as an AE is not required during the first 24 hours postdose and may not occur for low-grade reactions. Injection site reaction data are recorded separately by patient reported injection site reaction assessments and also by investigator reported injection site reactions. These data will be reported separately and may not be identical.

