3.7.1 Adverse Events and Serious Adverse Events

Treatment emergent AEs (TEAEs) and Treatment emergent serious AEs (TESAEs) are events that had an onset after the first dose of investigational product. TEAEs and TESAEs will be coded with the most updated version of the Medical Dictionary for Regulatory Activities (MedDRA), and the incidence, severity and relationship to investigational product will be summarized by treatment group and MEDI5884 overall for each MedDRA system organ class and preferred term reported. Adverse events leading to discontinuation, AEs leading to death, and deaths will also be summarized. Specific AEs will be counted once for each subject when calculating percentages. In addition, if the same AE occurs multiple times within a subject, the highest severity and level of relationship observed will be reported. All TEAEs and TESAEs will be summarized overall, as well as categorized by MedDRA system organ class and preferred term. Injection site assessments (redness, swelling, and pain) regardless reported as AEs or not will also be summarized.

Subjects with potential immunogenicity related TEAEs for immune complex diseases, allergic reactions, and injection site reactions according to Standardized MedDRA Queries (SMQ) will be summarized. The US Food and Drug Administration has requested that safety data be analyzed for this study according to the following SMQs: Systemic lupus erythematosus (broad and narrow terms); vasculitis (broad and narrow terms); Guillain-Barre syndrome (narrow terms) and allergic reactions (narrow SMQs for anaphylactic reaction, angioedema, severe cutaneous adverse reaction, anaphylactic/anaphylactoid shock conditions and hypersensitivity). Injection site reactions will be assessed using the following high level MedDRA (HLT) terms: administration site reactions, application and instillation site

reactions, infusion site reactions, and injection site reactions. These terms will be updated to the current version of MedDRA.

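### The 24-hour injection-site worksheet cannot document the Grade 2 pain criterion that requires more than 24 hours of analgesic use

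*Protocol*

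**What the plan says.** Under Protocol Section 4.3.2.5, the subject records on a worksheet "whether or not an injection site reaction has occurred at any injection site during the 24 hours after each dose of investigational product". If so, the subject measures redness and swelling and grades pain by Table 4.3.2.5-1 "for the maximum observation at any injection site". The text after the table again treats 24 hours as the collection period.

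The table grades pain as follows:
- Grade 1: "Does not interfere with activity"
- Grade 2: "Repeated use of non-narcotic pain reliever > 24 hours or interferes with activity"
- Grade 3: "Any use of narcotic pain reliever or prevents daily activity"
- Grade 4: an emergency room visit or a hospital admission

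The same section sends reactions occurring later than 24 hours to adverse event recording. For the earlier period it says that "reporting of injection site reactions as an AE is not required during the first 24 hours postdose and may not occur for low-grade reactions". It adds that subject-reported and investigator-reported reactions are presented apart and need not agree.

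SAP Section 3.7.1 states: "Injection site assessments (redness, swelling, and pain) regardless reported as AEs or not will also be summarized". It gives no rule for deriving the pain grade.

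**The concern.** The recording window and one of the grading criteria do not fit together. The subject is asked for a grade that depends partly on how long analgesics were used, but the form covers a shorter time than that criterion requires. Someone who takes a simple analgesic repeatedly for two days while keeping up normal activity meets the written definition of Grade 2. A worksheet that closes at 24 hours shows only pain without interference, which is Grade 1.

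Tolerability of repeated subcutaneous dosing is part of the primary objective, and the worksheet is the only source that applies this pain scale. If sites handle the mismatch differently, one closing the grade at 24 hours and another waiting, the same experience can be graded differently in the same table.

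**Working it through.** The plan states no figure on this point, so the check compares what the window can show with what each grade requires.

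**Inputs**, all from Protocol Section 4.3.2.5:
- worksheet window: 24 hours after each dose
- duration required by the analgesic route to Grade 2: more than 24 hours
- the two routes to Grade 2 are joined by *or*

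**Step 1. Longest use the worksheet can show.** If analgesic use starts t hours after the dose (t ≥ 0), the longest duration visible inside the window is 24 − t ≤ 24 hours. The criterion requires more than 24 hours, so no value of t satisfies it. The result is the same if the criterion is read as use continuing later than 24 hours after the dose, because that use also lies outside the window.

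**Step 2. Which routes remain.**

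| Grade | Route | Duration needed | Can a 24-hour record show it? |
|---|---|---|---|
| 1 | no interference with activity | none | yes |
| 2 | repeated non-narcotic analgesic | > 24 hours | no |
| 2 | interference with activity | none | yes |
| 3 | any narcotic, or daily activity prevented | none | yes |
| 4 | emergency room visit or admission | none | yes |

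**Step 3. Who is affected.** A subject is placed one grade too low only if all of these hold:
- repeated non-narcotic use lasts beyond 24 hours
- pain does not interfere with activity
- no Grade 3 or Grade 4 feature is present

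For the two-day example, use is 2 × 24 = 48 hours, which exceeds 24. The table gives Grade 2, but the window shows at most 24 hours and the worksheet gives Grade 1.

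**Step 4. Does another data stream supply the missing grade?**
- *Adverse events.* AE entry is optional for reactions in the first 24 hours. The rule for later reactions speaks of when they occur and does not say how a reaction that starts inside the window and persists is handled. AEs are graded on the general scale in Section 10.3.1.4, whose Grade 1 allows minimal treatment, so the same subject could be Grade 1 there too.
- *Concomitant medications.* Section 4.7 has all medication recorded in the eCRF, and Table 4.2.2-1 schedules that assessment at each listed visit. Neither document links these records to the pain grade.
- *Site query.* Section 4.3.2.5 has the site question the subject when the worksheet is not returned. It does not extend the window or ask about analgesic duration.

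**Step 5. Size.** With 20 subjects per group and three doses, there are 20 × 3 = 60 worksheets per group and 120 × 3 = 360 in all. Three doses is an assumption: the regimen table is redacted, and Section 4.1.6 refers to Doses 2 or 3. These are denominators only. Neither document gives a rate for the subset in Step 3, so no count of misgraded worksheets follows.

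**The case against.** The strongest reply is that the trial does follow pain past 24 hours. Later reactions become AEs, all treatment-emergent events must be reported (Section 5.4.1), and every medication goes into the eCRF. Section 4.7.2 also tells subjects to consult the investigator before taking even over-the-counter products. Prolonged analgesic use should therefore come to the site's notice. This stands in part. The information probably exists in the database, which makes the repair cheap, but nothing carries it into the pain grade.

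Second, the section fixes when a reaction must occur and does not expressly say that grading closes at hour 24. Table 4.2.2-1 places injection-site assessments at visits following the dosing visits. The visit days and the footnote to that row cannot be seen in the public text, and the footnote may say more. The Amendment 2 log describes the footnote added then as concerning measurement over the 24 hours after administration. A reader might infer that the criterion can never be met in this trial. That is too strong. What the visible text supports is that a 24-hour record cannot document it.

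Third, a reader might infer that moderate pain in general is graded too low. It is not, because interference with activity is enough for Grade 2 and needs no duration.

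Fourth, SAP Section 3.7 measures the primary safety endpoint by the incidence of TEAEs and TESAEs, keeps safety descriptive and plans no formal comparison. This is right, and it limits the consequence. Presenting subject and investigator data apart is a disclosed choice and not a fault in itself.

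**Conclusion.** The point holds in a narrow form. The worksheet window and the analgesic-duration criterion in Table 4.3.2.5-1 are inconsistent. Followed as written, the rule records as Grade 1 any subject with repeated non-narcotic use beyond 24 hours, no interference with activity and no Grade 3 or 4 feature. The error is one grade, in one direction, and confined to the worksheet summary. How many subjects it touches is unknown.

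A reader might go on to infer that dose groups with longer-lasting pain would look too favourable, or multiply 60 worksheets per group by an assumed rate to get a number misgraded. The documents give no pain duration, analgesic rate or difference between groups, so neither inference is supported. No sample size, power or alpha figure is affected.

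This rests on two assumptions: that the unseen schedule footnote does not extend the pain record past 24 hours, and that the SAP summary of pain uses the grade as recorded on the worksheet.

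**What to change.** In Protocol Section 4.3.2.5, reconcile the worksheet instruction with the text on later reactions. State that, for a reaction starting within 24 hours, the pain grade is finalised at the next scheduled contact using the date and time of last analgesic use for injection-site pain. One added worksheet item can supply this, or the concomitant-medication dates in the eCRF where available. Say also whether the 24 hours run from first use or from the dose, since the derivation needs a start point. Redness and swelling can keep the 24-hour window.

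In SAP Section 3.7.1, state that Grade 2 pain is derived from that information. If the 24-hour cut-off stays, footnote the pain table to say that the analgesic-duration criterion was not assessable.

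The Amendment 4 log notes that all subjects had by then finished dosing. For data already collected, the usable options are therefore derivation from concomitant-medication dates or the footnote; the worksheet item would serve later use of the form.

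The cost is one worksheet and eCRF item and a sentence in each document, with no new visit. The downside is slightly more subject reporting and possibly more Grade 2 entries.
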